9.0 Procedures Involved

- 9.1 We will conduct a three arm physician randomized study trial in the emergency department at Northwestern to measure the effect of an EHR-based, Medication Complete Communication (EMC²) and EMC²+SMS text reminder strategies on increasing provider counseling, increasing patient understanding of risks associated with newly prescribed opioid medications, and demonstrating more appropriate, safe use of prescribed high-risk opioid medications. English speaking patients who are prescribed hydrocodone-acetaminophen will be recruited and assessed with phone interviews at 2-4 days, 7-14 days and 1 month.
- 9.2 Provider Randomization. To optimize the likelihood of obtaining similar populations in each intervention arm, providers that have consented to participation in the study will be placed into 4 strata depending on their role (attending versus resident) and historical volume of opioids prescribed. [name], blinded to provider identity will randomly assign providers within each stratum to each of three study arms using a random number generator. We will reveal provider identities after randomization is complete.

Provider role and training. All providers will be informed of the possible interventions that their patients may receive (e.g., Universal Medication Schedule sig codes (See below on page 9), Medication Sheet, Text reminders, and emails to PCP as well as any changes such randomization may cause to the providers workflow (i.e, for some providers, intermittent pop-ups reminding them to counsel patients). Providers will be told that they will be assigned to either the usual care or one of two intervention groups. The providers who are assigned to the intervention groups will be trained on how to 1) prescribe medications with the EMS instructions from the “favorites” list and 2) how the other components of the intervention will automatically generate (MedSheet, emessage to PCP).

The initial study visit (baseline) will be conducted at the time of patient enrollment. Following this baseline interview, RAs will conduct three telephone interviews (at 2-4 days post-baseline, 7-14 days post-baseline and at one month post-baseline). The first two assessments (at enrollment and 2-4day follow-up call) have been included to closely track patient recall of counseling and knowledge, while the latter two assessments (7-14 day follow-up call and 1 month follow-up call) are included to assess decay of knowledge, safe use, storage of medications and demonstrated dosing. The final call (one month post-baseline) will assess disposal of

EHR-Based Medication Complete Communication (EMC²) Strategy to Promote Safe Opioid Use: A Physician Randomized Trial

medications and determine if patients have received additional opioid pain relievers from other providers.

Baseline Interview. At the time of enrollment, the RA will ask the participant to indicate the best days and times to call within a 2-4 day range. A \$5 Gift card given to the participant for completion of enrollment tasks.

First Study (2-4 Day) Phone Call. The study phone call will be conducted at a time of convenience for the patient, however still within a 2-4 day range post-baseline. Additionally during this phone call, the RA will either confirm or schedule the 7-14 day follow-up call. A \$10 Gift card will be mailed to the participant for completion of first phone call.

Second Study (7-14 Day) Phone Call. The second phone call will be conducted at a time of convenience for the patient, however still within 7-14 day range post-baseline. Patients will be compensated for their time to complete the call with a \$20 gift card which will be mailed to the participant upon completing the call. Patients will also be asked to mail back their de-identified medication diary using the prepaid envelope provided at baseline.

Third/Final Study (1 Month) Phone Call. The final study phone call will be conducted at a time of convenience for the patient, however still within 1-month post-baseline. (See Attached Interview script)

Intervention Patients with physicians randomized to the EMC² arm will receive the 5-part EMC2 intervention.

[figure not shown]
[1] Funded by AHRQ [R18HS17220], we created single-page, plain language medication information sheets with content appropriately sequenced from a patient's perspective (drug name, indication, purpose/benefit, how to take, for how long, when to call your doctor, when to stop taking and call your doctor, important information) and following other health literacy best practices.

[2] The medication sig ('sig' is short for *signa*, which in Latin means "write") contains directions to the patient (e.g.: "take one pill every 8 hours). We have shown that we are able to replace existing EHR default sigs for the top 300 medicines prescribed in primary care with UMS instructions [R21CA132771] and have evaluated the use of UMS sigs in actual pharmacy practice [R01HS017687] for non-PRN medications. The UMS sig for PRN medications has been evaluated in two studies (California Healthcare Foundation, McNeil Consumer Healthcare), and we have found that patients with the UMS sig for PRN dosing (Take-Wait-Stop label) were less likely to exceed the maximum daily recommended

EHR-Based Medication Complete Communication (EMC²) Strategy to Promote Safe Opioid Use: A Physician Randomized Trial

dose of their opioid prescription. The UMS Sig for the opioids in question in this study will change the text on the prescription bottle as demonstrated in Figure 1

Figure 1: Standard label (left), UMS Take-Wait-Stop label (right)

[3] In addition to the tools that the patient receives, the EHR will automate communication to the patient's prescribing ED physician, reminding them to counsel the patient with a pop-up window.

[4] Additionally, there will be communication to the dispensing pharmacist by making a note on the paper-prescription requesting the pharmacist consider counseling the patient.

[5] Finally, there will be a notification to the primary care physician (PCP) if the patient has a PCP in the Northwestern system. This notification was initially conceptualized as being automated when the inpatient and outpatient Cerner systems were compatible. Since the switch of the outpatient Northwestern Medicine offices to the EPIC EHR, this automated function is not longer available. Therefore, the RAs enrolling the subjects will note if the patient has a Northwestern Medicine physician. If the patient enrolled for follow-up has a physician in the system, the RA will manually log-in to the outpatient EPIC interface (with write functionality) and send the PCP an inbox message with the following sample text: "Your patient NAME, DOB was seen in the Northwestern Emergency Department on MONTH DATE, 20XX. They received a prescription for Hydrocodone-Acetaminophen (DOSE, TIMING, NUMBER OF TABS). When you see this patient for a follow-up appointment, please consider counseling them about the safe use of this medication. For additional information about your patient's visit to the Emergency Department, you may access the Emergency Department Note and Depart Summary. The Depart Summary will also contain a copy of the information sheet that your patient received about their new prescription pain medication."

EHR-Based Medication Complete Communication (EMC²) Strategy to Promote Safe Opioid Use: A Physician Randomized Trial

[Note: Neither the Pharmacist nor the PCP receiving the messages to “consider counseling the patient” are required to take any action as part of the intervention. The study is designed with the ED as point of care and we will be assessing implementation to gauge the response to these messages among those PCPs and pharmacist who received them; however, these providers are not required to do anything as part of the study or intervention.]

Patients with ED physicians randomized to the EMC² +SMS Text reminder arm will receive the above-described 5 components of the EMC² intervention, and also will receive daily text reminders for one week (7 messages) following the new prescription for an opioid pain reliever (only consented patients). The premise for the 1-week timeframe is to help patients remember precautions regarding safe use during the time they are taking the medication (average ED Rx for opioids is from pilot data is 18 tabs). Furthermore, SMS text reminders that would continue indefinitely are at risk for either being ignored, irritating patients, and/or adding an unnecessary expense to patients (i.e., patient does not have an unlimited texting plan, further challenging sustainability). Messages sent early in the week will focus on topics such as safe storage and use; those sent near the end of the week will focus on topics such as disposal and pill sharing. We will schedule EMC² text messages to arrive mid-day (12:00pm to 5:00pm), based on patient preference. (See appendix for sample text messages)

9.3 Procedures to monitor safety and minimize risk.

As a part of all of the time points of follow-up, the RAs will have a checklist of potentially dangerous behaviors related to opioids and if these items are noted in the course of data collection the RAs have a set protocol to follow. (see safety protocol attached)

9.4 The drug hydrocodone-acetaminophen is the topic of the research; however it is not being used in the research—the intervention is focused on education about this medication and the study will not change the drug, dose, frequency, quantity or refills that the ED physician selects in the course of their normal clinical care.

Sources of Materials:

Electronic Health Record (EHR): Patient information and outcomes will be extracted from the EHR (demographics, ED return visits and re-admissions). Re-admissions and re-visits to the hospital and ED data will be abstracted from medical records for all patients enrolled into the study, as well as all patients prescribed an opioid during the recruitment period of 18-months.

EHR-Based Medication Complete Communication (EMC²) Strategy to Promote Safe Opioid Use: A Physician Randomized Trial

Illinois Prescription Monitoring Program (ILPMP): We will obtain data from the ILPMP on medication fill date, subsequent refills of the prescribed opioid, and new prescriptions for other controlled substances.

All personal health information will be kept behind organizations' firewalls. Analytic databases will be created with removal of all personal health information; these will then be sent to Northwestern investigators for analysis.

Patient in-person enrollment & follow-up phone interviews: Interviews include assessments of health literacy skills, safe medication use, and medication understanding, among others.

Provider surveys: Both the ED providers and the follow-up providers (PCP and Pharmacists) will be surveyed to assess their reactions to the intervention via electronic and mail survey.

10.0 Data and Specimen Banking

- 10.1 Data will be stored for up to 5 years after study completion for data analysis and publication of study results. At that time, all identifiers will be destroyed, but de-identified data will be retained. Data will be stored on Northwestern encrypted servers and access will be granted through the PI.
- 10.2 The clinical data, interview data and prescription refill data noted above will be stored.
- 10.3 Data will not be released.

11.0 Data and Specimen Management

- 11.1 AIM 1 Analysis Plan. The proposed trial uses a cluster-randomized design where the prescribing physician is the unit of randomization. We will randomize approximately 150 physicians (50 attending physicians, 100 EM resident physicians and mid-level providers) to three intervention arms (usual care, EMC², and EMC² + SMS text reminders). The estimate of 150 includes a base of 100 providers with an estimate of approximately 50 new providers over the course of the 18 months of recruitment (e.g. 15 new residents in 2015, 15 new residents in 2016 and new attending hires). At any given time, we estimate that 100 providers will be actively involved in the study, resulting in approximately 33-34 physicians per arm. Physicians will be stratified by provider role (i.e., attending vs. resident) and randomly assigned to one of the three arms with an equal number assigned to each. We will accrue approximately 12 patients per physician; we conservatively anticipate at least 54% retention for the phone call follow-up 7-14 days post prescription. These estimates will result in 1500 participants recruited with an anticipated

EHR-Based Medication Complete Communication (EMC²) Strategy to Promote Safe Opioid Use: A Physician Randomized Trial

minimum of 816 patients at in-person follow-up (272 per arm, 8 per physician) available for primary data analysis.

To ensure adequate balance across the 3 arms, potential confounders including socio-demographic characteristics, comorbidities, regimen complexity (i.e., # of medications, total pills taken daily), health literacy level, and history of opioid use will be compared using one-way ANOVA models and χ^2 tests, as appropriate. Covariates with significant differences (p -value $< .05$) across treatment groups will be included in the generalized linear mixed models (GLMMs) to adjust for the group differences as described below. We note that detected differences may be physician-specific, so if we observe differences across the treatment arms, we will explore whether the difference might be attributable to individual physicians.

Demonstrated safe use by not exceeding the maximum dose is the primary outcome of interest for Aim 1 (H_3), with higher reported rates of provider counseling and greater understanding of risks relevant to hypotheses of secondary interest for Aim 1 (H_1, H_2). We will use GLMMs for analyses of the data, specifying the logit link function for the binary outcomes using xtmixed in Stata (v.12.1). The 3-category treatment group variable will be the independent variable of primary interest and modeled as a fixed effect with the usual care group specified as the reference. We will also include fixed effects for any potential confounding covariates noted in the descriptive studies that were not accounted for in randomization. Random effects will be included for each physician to account for intra-physician correlation among participants. For all GLMM analyses we will report point estimates and corresponding 95% confidence intervals. We will examine and report the extent to which the random effects suggest correlation of outcomes within physicians.

Measures taken to minimize bias. For the randomization scheme of this study, physician is the unit of randomization rather than patient. With healthcare interventions and quality improvement projects, such as the one proposed herein, there are no other ways to evaluate an automated EHR process than to “turn them on.” This is why the randomization will occur at the physician level rather than the patient level. This process will result in trickle down of aspects of the EMC² intervention (but not SMS texting) to patients seen by the consented provider, but not enrolled in the study for follow-up purposes (e.g., on overnight shifts).

Level of significance to be used. We will use a two-sided 5% significance test

Stopping rules. We will stop enrollment once we have reached the 1500 patient enrolled maximum.

EHR-Based Medication Complete Communication (EMC²) Strategy to Promote Safe Opioid Use: A Physician Randomized Trial

Procedures for reporting deviations from the original plan. Any deviations involving human subjects will be submitted to the IRB for review before being implemented.

Selection of subjects for inclusion in the analysis. All subjects with complete information (e.g., at least 80% completion of interview instrument) will be used in the analysis.

AIM 2 Analysis Plan. Following completion of enrollment, we will determine the extent to which the interventions were implemented as planned (a process evaluation) in the two intervention arms. In the EMC² and EMC² + SMS text reminder arms, we will collect EHR data on prescriptions and discharge summaries to assess if patients actually received the new prescriptions with the UMS (Take-Wait-Stop) sig, and review pill bottle information during the 7-14 day phone call to determine if the sigs were translated accordingly onto patients' drug labels. For the EMC² + SMS text reminder arm, we will ask patients at all follow-up intervals if they received the text messages. For those electing to turn off the service, we will qualitatively explore and code reasons why.

Usability of the EHR interventions will be assessed among the ED physicians and follow-up providers (PCPs and pharmacists) via survey.

AIM 3 Analysis Plan. We will directly measure and assess the provider perspective costs of running the two EMC² interventions. Specifically, we will estimate the incremental cost of the interventions relative to usual care from the perspective of the ED implementing these systems. The primary costs of running the EMC² intervention involve the limited expenses around printing (printer ink, paper, staff time). However, we will include estimates for minimal programming maintenance and will test the sensitivity of results to changes in the maintenance requirements in terms of programmer hours. We also will separately track development costs for software and other programming requirements based on programmer hours. The greater cost, in terms of running the program, will be that for the SMS text services, which will include the nominal monthly cost as well as staff time to schedule the SMS text reminders after the initial ED visits. For study purposes, the RA will do this task; however, we will have record on a daily basis in a study database (Microsoft Office Access, Microsoft Corp.) the number of minutes spent programming the SMS text reminders. This record will allow us to estimate the direct staff costs of this component by combining time with wage estimates. We will test the sensitivity of costs to different assumptions about the potential use of variable staff (nurse, clerk, medical assistant) using different salaries but assuming the same proficiency in terms of time required. Further we will assess the sensitivity of the

EHR-Based Medication Complete Communication (EMC²) Strategy to Promote Safe Opioid Use: A Physician Randomized Trial

estimates to different proficiency levels that could arise from learning by doing.

To achieve Aim 3, [name], at UIC, will help in analyzing time and resource use related to the intervention. Any data that he would receive would be anonymous and would not contain any patient PHI. Instead, the data would involve counts of hours spent, and materials used, in creating and implementing the intervention.

11.2 Rationale for choice of sample size, power considerations. The sample size for this study was based on pairwise comparisons between the two intervention arms compared to usual care (i.e., usual care vs. EMC² and usual care vs. EMC² + SMS). This calculation was based on the primary outcome of demonstrating safe use by not exceeding the maximum recommended dose at the 7-14 day phone follow-up interview.

Conservatively estimating 54% retention rate for 7-14 day follow-up call, we will have 82% to detect a difference of 11.8% between each intervention and the usual care arm assuming a Type I error of 2.5% to account for the two comparisons. An intraclass correlation coefficient (ICC) of 0.001 was used because we do not expect patient outcomes to be influenced by the clustering of physicians due to patients being randomly assigned a physician upon ED entrance and physicians typically working a random assortment of shifts.

With the sample size set by the primary outcome of demonstrated safe use by not exceeding the maximum dose, we also show detectable effects for the secondary outcomes in Table 3, assuming at least 80% power, a Type 1 error rate of 2.5%, an ICC of 0.001, and usual care estimates from prior studies.

11.3 Data Safeguarding Procedures. Any information that could allow identification of individual patients, including the master list, will be kept strictly confidential. In order to preserve participants' confidentiality rights, research subjects will be assigned study ID numbers that will be used to identify all the information collected. A master study tracking database will contain information linking participants to their study ID numbers. This database will be on RedCap and is both encrypted and password protected and only accessible by approved study personnel at Northwestern. Grant file access permissions will only be given to specific approved research personnel, as designated by the PI.

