Statistical Analysis Plan

EHR-Based Medication Complete Communication Strategy to Promote Safe Opioid Use

NCT02431793

Document Date: June 7, 2019

Analysis Plan – Main Manuscript

Descriptive statistics were calculated for all socio-demographic, ED visit, and opioid prescription characteristics. Chi-square, one-way Analysis of Variance (ANOVA), and Wilcoxon rank-sum tests were used, as appropriate, to test for balanced randomization. An inter-cluster correlation assessment was conducted to assess the degree of independence among individuals in the same cluster. We used generalized linear mixed models on all outcomes adjusting for physician clustering. Models were run for dichotomous outcomes (safe demonstrated dosing, safe actual dosing; adjusted odds ratios [ORs] reported) and for continuous composite knowledge score (adjusted mean differences reported). Examination for possible associations between patient characteristics and outcome variables revealed significant was conducted, and all models controlled for covariates that related to the outcome. To isolate the effect of the SMS texting portion of the intervention from the EMC² EHR embedded tools a generalized linear mixed model was conducted utilizing two dummy variables (“emc2” for patients in both intervention arms, “text” for patients in EMC² +SMS arm) rather than the study arms on the primary and secondary outcomes as well as the individual knowledge or behavior questions linked to each text message. Significance for all analyses was set at $p < 0.025$ to adjust for multiple testing.

All analyses were first conducted using an intent-to-treat approach. Subsequently, because some patients did not receive one or more pieces of the intervention, the primary outcome was analyzed per-protocol, where the same methodology described previously was used but applied only to patients who successfully received all patient-facing pieces of the intervention. Patients in the EMC² arm were included in the per-protocol analysis if they received the MedSheet and the patient-centered TWS prescription wording on their bottle. Those in the EMC² +SMS arm were included in the per-protocol analysis if they received the MedSheet, TWS prescription wording on bottle, successfully enrolled in SMS texting, and received all seven text messages.

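### The stated primary model leaves out the provider strata used in randomisation (negligible at the protocol's ICC), and the SAP changes the covariate rule without saying so

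*Protocol*

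**What the plan says.** Protocol 9.2 has consenting providers "placed into 4 strata depending on their role (attending versus resident) and historical volume of opioids prescribed", then assigned at random to the three arms within each stratum. Protocol 11.1 describes the same step with one factor: "Physicians will be stratified by provider role (i.e., attending vs. resident) and randomly assigned to one of the three arms", in equal numbers per arm.

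The Aim 1 model in 11.1 is a logistic mixed model with treatment as a fixed effect and a random effect for physician. On further terms it says: "We will also include fixed effects for any potential confounding covariates noted in the descriptive studies that were not accounted for in randomization". The candidates listed for balance testing in 11.1 are patient-level: "potential confounders including socio-demographic characteristics, comorbidities, regimen complexity", then health literacy and opioid history. Those that differ between arms at p<.05 "will be included in the generalized linear mixed models (GLMMs) to adjust for the group differences as described below".

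The SAP, dated June 2019 and written in the past tense, keeps balance tests but does not link them to the model. It adjusts for physician clustering and reports that "all models controlled for covariates that related to the outcome". The preceding sentence is garbled, but it places the screening among patient characteristics: "Examination for possible associations between patient characteristics and outcome variables revealed significant was conducted". Role, prescribing volume and strata do not appear in the SAP.

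**The concern.** An analysis should normally reflect the groups within which a trial randomises. Stratification is meant to keep variation between strata out of the treatment comparison. A model without the strata still counts that variation as error. The physician random effect does not repair this, because it treats the difference between, say, attendings and residents as more random physician-to-physician noise. What is at stake is precision, and perhaps a test that rejects less often than its nominal level.

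The second issue is traceability. The protocol selects covariates on chance imbalance and the SAP selects them on relation to outcome. No passage says that one replaced the other, which covariates were selected, or what threshold was used. A reader cannot tell what the adjusted odds ratios are conditional on.

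**Working it through.** **Inputs from the documents.** 272 evaluable patients per arm and 8 per physician (11.1), hence 272/8 = 34 physicians per arm; a difference of 11.8 points, 82% power, type I error 2.5% per comparison and ICC 0.001 (11.2). I take the 2.5% as two-sided, so z = 2.241.

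**Assumptions.** f, the share of between-physician variance that the strata explain, is set at 0.5, with 0.2 and 1 as the range. ICCs of 0.01 and 0.05 are alternatives that the documents do not state.

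**The plan's own figure.** No usual-care rate is given for the primary outcome, so I solved for it. The design effect is 1 + 7 × 0.001 = 1.007. With 68.1% v 79.9% safe use, the variance sum is 0.681 × 0.319 + 0.799 × 0.201 = 0.378, and the standard error is √(0.378 × 1.007/272) = 0.0374. Then 0.118/0.0374 − 2.241 = 0.91, which is 82% power. The stated figure is therefore matched, but only with this inferred rate.

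**Effect of the strata.** Without strata, the model's standard error uses DE = 1 + (m − 1) × ICC. If arms are balanced within strata, the true variance uses DE* = 1 + (m − 1) × ICC × (1 − f). Then:

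- size without strata = 2 × [1 − Φ(2.241 × √(DE/DE*))]
- power without strata = Φ[(0.118 − 2.241 × SE)/SE*]
- power with strata = Φ[0.118/SE* − 2.241]

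For m = 8 and f = 0.5:

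| ICC | DE | DE* | Size, omitted | Power, omitted | Power, included | Gain (points) |
|---|---|---|---|---|---|---|
| 0.001 (stated) | 1.007 | 1.0035 | 2.5% | 82.0% | 82.1% | 0.1 |
| 0.01 (assumed) | 1.070 | 1.035 | 2.3% | 79.8% | 80.8% | 1.0 |
| 0.05 (assumed) | 1.350 | 1.175 | 1.6% | 69.8% | 75.2% | 5.4 |

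At the three ICCs in turn, the gains are 0.0, 0.4 and 2.1 points with f = 0.2, and 0.2, 2.1 and 10.9 with f = 1. Section 11.1 also says "We will randomize approximately 150 physicians". If the 816 patients spread over all of them, m = 816/150 = 5.44, and the gains at f = 0.5 fall to 0.1, 0.7 and 3.4 points.

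**Check by simulation.** A random-intercept logistic model was fitted to 102 physicians with 8 patients each, f = 0.5, with 1,000 paired runs. Adding strata to the SAP-type model changed power by 0.0 (SE 0.2), +0.3 (SE 0.3) and +4.5 (SE 0.7) points at the three ICCs. Only the last differs clearly from zero.

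**Is the test conservative?** That depends on balance within strata. In cluster-level simulations under the null at ICC 0.05 and f = 0.5, the model without strata had size 1.3% to 1.6% with arms balanced within strata. Under simple randomisation within strata it was 2.4% to 2.7%, close to the nominal 2.5%. Section 11.1 promises equal numbers per arm, which suggests balance. Section 9.2 mentions only a random number generator, no block scheme is given, and about 50 of the 150 providers join during recruitment.

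**The case against.** The strongest reply is that nothing of consequence follows at the only ICC the documents state. The loss there is 0.1 power point, and a clear effect needs an ICC fifty times larger plus an assumption about f. That stands, and it sets the severity. The protocol also promises to report within-physician correlation, and the SAP says it was assessed, so the team can already tell whether the strata matter.

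A reader might infer that the SAP excludes the strata. It does not. Its operative clause covers covariates related to outcome, and the restriction to patient characteristics comes from the garbled sentence before it. The SAP is silent; the protocol wording is what excludes them.

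A reader might also infer that 11.1's imbalance rule cost the trial power, or that a fixed covariate list should now be preferred. Neither is supported. The SAP reports using outcome-related covariates, so any cost of the imbalance rule belongs to an analysis that the SAP does not describe. In simulations with assumed prognostic strengths, adjusting for all of eight candidates instead of the SAP's selection changed power by +0.3, +0.2 and −0.2 points (SE 0.2), which is no stable gain. For completed analyses, prespecification is no longer available as a reason.

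Finally, adding the strata is not purely mechanical. The documents do not say how historical volume was set for providers who joined later. Section 9.2 contrasts attendings with residents without placing mid-level providers, whom 11.1 groups with residents only in its head count.

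**Conclusion.** The point holds as a minor one. The protocol's primary model, as worded, omits the factors used to randomise providers, and the SAP does not say whether they were included. If they predict outcome, precision is lost: about 0.1 power point at ICC 0.001, about 1 at 0.01 and about 5 at 0.05, given 8 patients per physician and strata explaining half of between-physician variance. Those two larger ICCs and that share are assumptions.

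It would be too strong to say that the result is biased, that type I error is inflated, or that the test is certainly conservative. Randomisation protects the comparison with or without the strata terms, and conservatism requires balance within strata, which is suggested but not guaranteed.

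The change of covariate rule is a disclosure point only. The SAP rule is naturally read as governing, and selecting on relation to outcome is the sounder of the two rules. What is missing is a statement that it replaced the protocol's rule, and what it selected.

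**What to change.** 1. Reconcile 9.2 and 11.1 on the stratification factors. State the strata actually used, including how mid-level providers and the roughly 50 later-joining providers were classed, and whether allocation was blocked within strata.
2. State whether the reported models included the strata. If not, add them as fixed effects in every mixed model and present the results as a post hoc sensitivity analysis, because the SAP describes completed analyses. Give the observed ICC alongside.
3. State that the SAP's outcome-related rule replaced 11.1's p<.05 imbalance rule. List the covariates selected for each outcome and the threshold used.

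The cost is up to three extra model terms (four strata less one), one rerun and a few sentences. No design change is needed. No new patient data are needed either, provided each provider's stratum can be recovered from the randomisation records.
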